11.3 Primary and Secondary Data, Modeling, and Data Analysis

11.3.1 Outcome Measures

Blood for PK sampling will be collected at select study visits, and before the morning dose of CVC/placebo, as per protocol for CVC and ART. Trough ART levels will be determined for all participants at pre-entry and weeks 4, 8, 12, and 24. For those randomized to active drug, trough levels for CVC will be determined at weeks 4, 8, 12, and 24.

Only drug concentration levels determined from samples obtained at steady state (no missed doses within the preceding 4 days) and no more than 14 hours post last EFV-based ART or 26 hours post last non-EFV based ART and CVC/placebo for CVC dose will be used in analyses.

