5.1.2 Administration

CVC 150 mg or Placebo: Administered as one 150-mg tablet/placebo.

CVC 300 mg or Placebo: Administered as two 150-mg tablets/placebo.

The appropriate dose of CVC or placebo for CVC will be administered by mouth once a day with food. The dose should be taken as close to the same time of day as possible.

For participants who are on EFV-based regimen, CVC or placebo for CVC will be administered in the morning with food.

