6.3.10 Pharmacokinetic Studies

At each visit indicated in [section 6.1](#), a single PK sample will be drawn and stored.

Participants should be stable on ART for at least 10 days (i.e., no ART regimen change for 10 days) prior to PK draws. The ART dose prior to the PK evaluations should be given as close to 12 hours prior to the PK evaluation as is feasible. Blood should be drawn before the morning dose of CVC/CVC placebo (as applicable) and ART. In the case where a morning CVC/CVC placebo or ART dose is taken prior to the trough measurements or if any of the four preceding doses have been missed, the PK sampling should be rescheduled during the same week, if possible. If this is not possible, contact the A5415 CMC ([contact]) for guidance. Dates and times of the last four doses of ART and CVC will be recorded.

For processing and shipping instructions, refer to the A5415 LPC. Refer to [section 11.0](#) for assay details.

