9.1.1 Descriptive Statistics of CVC Trough Estimates by ART Class

Analysis set(s): Complete case set (cenicriviroc arm only)
Grouped by: a) ART Class (INSTI, NNRTI, both); b) ART Agent

Table	CVC Trough Estimates by ART Class / Agent
Characteristic	Summary Statistic(s)
Participant-level average CVC trough concentration	Median (Q1, Q3), and P10, P90
CVC trough concentration by week	Median (Q1, Q3), and P10, P90

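### Drug levels taken about 12 h and about 24 h after a once-daily dose both count as troughs, and the SAP's trough tables, covariate and paired test do not adjust for the difference

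*Protocol*

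**What the plan says.** **Which samples count.** Protocol 11.3.1 uses levels obtained at steady state and "no more than 14 hours post last EFV-based ART or 26 hours post last non-EFV based ART and CVC/placebo for CVC dose". These are upper limits only. It also places collection before the morning CVC or placebo dose.

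**What sites are told.** Protocol 6.3.10 says: "The ART dose prior to the PK evaluations should be given as close to 12 hours prior to the PK evaluation as is feasible". This is not limited to efavirenz (EFV) and does not cover CVC. The next sentence reads: "Blood should be drawn before the morning dose of CVC/CVC placebo (as applicable) and ART". If a morning dose has already been taken, "the PK sampling should be rescheduled during the same week, if possible". The same section adds: "Dates and times of the last four doses of ART and CVC will be recorded".

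**When CVC is taken.** Protocol 5.1.2: "The appropriate dose of CVC or placebo for CVC will be administered by mouth once a day with food", and "The dose should be taken as close to the same time of day as possible". Only participants on EFV are told to take it in the morning.

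**How levels are analysed.** Protocol 11.3.2 plans mixed models on log concentration, described as time-adjusted. It compares ART troughs between CVC and placebo participants, and with each participant's own pre-CVC level. In the SAP:

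- 9.1.1 tabulates "Participant-level average CVC trough concentration" and levels by week, as medians and percentiles by ART class and agent.
- 7.3 uses average CVC trough as a covariate for change in TBR.
- 9.1.2 compares pre-treatment and averaged on-treatment ART troughs by paired t-test for bictegravir, dolutegravir (DTG) and rilpivirine.
- 3.3 and 9 limit PK to the CVC arm.
- Only 9.1.3, the correlation with TBR, keeps the time-adjusted exposure estimate.

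**The concern.** A trough is the level at the end of the dosing interval. If time since dose varies by half an interval, part of the variation between samples reflects the clock, not the drug interaction.

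Objective 1.4.7 asks whether ART regimen changes CVC troughs and whether CVC changes ART troughs. Three SAP analyses are exposed: the CVC table by ART class or agent, the pre/on-treatment ART comparison, and the SAP 7.3 covariate. If dose-to-draw time differs between ART groups, the first contrast mixes timing with interaction. If it shifts between the single pre-entry sample and the on-study samples, the shift enters the estimated ART change directly, because the SAP has dropped the placebo comparison that would have shown it.

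**Working it through.** The documents give no sample size, power or precision for the PK objectives, so there is no stated figure to reproduce. The check has two parts: which samples the rules admit, and how large the timing error could be.

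**1. Rules side by side, for a once-daily drug and a morning visit**

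| Dosing pattern | Hours since dose | 12 h target (ART only) | Pre-morning-dose draw | 26 h limit |
|---|---|---|---|---|
| Evening | about 12 | met | met | passes |
| Morning, dose held | about 24 | not met | met | passes |
| Morning, dose already taken | a few | not met | not met, reschedule | passes |

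The first two rows both follow from compliant behaviour in at least one respect, and both are analysed as troughs. The 12 h target fits bedtime EFV and its 14 h limit, but SAP 9 does not list EFV among agents with at least 10 participants exposed. Once-daily dosing is stated for CVC (Protocol 5.1.2) and for DTG in the interaction study in Appendix I. The documents do not state it for bictegravir or rilpivirine.

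**2. Size**

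Inputs: DTG lowers CVC Cmin by 23% (Protocol 2.1, Study 110), a ratio of 0.77 or 1/0.77 = 1.30-fold. Half-life (h) is an assumption, shown from 12 to 48 h. Decline is taken as mono-exponential between 12 and 24 h.

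- Excess of a 12 h over a 24 h level: F = 2^(12/h).
- Half-life at which a full 12 h difference equals the DTG effect: 12 × ln 2 / ln(1/0.77) = 8.318/0.2614 = 31.8 h.
- Excess share of 12 h samples in the DTG group that would cancel the effect: 0.2614/ln F.
- Ratio seen with a 25% excess share: 0.77 × exp(0.25 × ln F).
- Log-scale SD added by a 50/50 mix that is the same in both groups: 0.5 × ln F.
- Error in a pre/on-treatment ART ratio if draws come 2 h sooner after the dose on study: 2^(2/h).

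| Half-life | F | Share to cancel 0.77 | Ratio seen, 25% excess | Added log SD, balanced | 2 h shift |
|---|---|---|---|---|---|
| 12 h | 2.00 | 38% | 0.92 | 0.35 | 1.12 |
| 18 h | 1.59 | 57% | 0.86 | 0.23 | 1.08 |
| 24 h | 1.41 | 75% | 0.84 | 0.17 | 1.06 |
| 36 h | 1.26 | not possible | 0.82 | 0.12 | 1.04 |
| 48 h | 1.19 | not possible | 0.80 | 0.09 | 1.03 |

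The larger EFV effect on CVC Cmin (48% reduction, 1/0.52 = 1.92-fold) is matched by a full 12 h difference only at half-lives up to 12 × ln 2 / ln(1/0.52) = 12.7 h.

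**The case against.** **The draw rule acts as a floor.** Drawing before the morning dose, and rescheduling if it was taken, largely protects morning dosers. This stands. A reader might infer that samples 2 h after a dose will be reported as troughs. The hours limit alone would admit them, but the draw rule makes them unlikely. The realistic case is evening dosing, and the documents do not say how common that is.

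**No cause of unequal timing is shown.** The same instructions apply at pre-entry and on study, and the only timing rule tied to ART is morning CVC for EFV users. This stands as a limit on bias: if timing is balanced across the groups or periods compared, the result is noise. It does not show that timing is balanced. CVC time of day is otherwise free, and Protocol 6.3.6 asks only for a consistent morning or afternoon draw, which does not fix time since dose.

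**Time adjustment is already planned.** Dose times are recorded, Protocol 11.3.2 and 11.4 foresee adjustment, and SAP 9.1.1 never calls its values raw. SAP 9 is also open to change, and an implementation plan will follow. This stands in part: the data for a correction exist. But time could mean hours since dose or study week, SAP 9.1.1 and 7.3 state no adjustment, and a paired t-test cannot supply one.

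**Timing swamps the interactions.** A reader might infer this from the factor of 2. The documents do not support it as a general statement: it needs a half-life they do not give and a strong imbalance between groups. The 28–36% rise in tenofovir exposure is not a fair yardstick either. It is AUC and Cmax from a single-dose study, and SAP 9.1.2 does not test tenofovir.

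**Conclusion.** The sampling rules conflict and admit mid-interval levels as troughs, and the SAP omits the adjustment in the analyses that need it. The weakest point is SAP 9.1.2, which has neither time adjustment nor a placebo contrast.

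The size is conditional. Under assumed half-lives of 12 to 48 h, a 12 h level is 2.0 to 1.19 times a 24 h level. A complete 12 h separation between groups matches or exceeds the 23% DTG effect only at half-lives up to about 32 h. A 25% excess of 12 h samples in the DTG group would move a true 0.77 to between 0.92 and 0.80. These figures rest on mono-exponential decline and on timing that differs between the groups compared.

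The consequence is limited to exploratory PK/PD objectives and one covariate in SAP 7.3. A reader might infer that the primary TBR comparison is at risk. It is not, because it uses no drug level.

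**What to change.** 1. In SAP 9.1.1, 9.1.2 and 7.3, use estimates from the Protocol 11.3.2 mixed model on log concentration. Define time-adjusted as hours since the last recorded dose of the drug being measured.
2. Report raw trough summaries only for samples inside a stated end-of-interval window for each drug, and keep all other timed samples in the model. For illustration, a 22–26 h window for a once-daily drug holds the error against a 24 h level to +12%/−11% at a 12 h half-life and about ±6% at 24 h.
3. Reconcile the 12 h target in Protocol 6.3.10 with the pre-dose draw in the same section and with the limits in 11.3.1. Which timing should apply is for the sponsor to settle.

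The SAP change is the one that can still help. Accrual closed on January 5, 2024, and 24 weeks plus the 14-day window ends in early July 2024, before SAP version 2.0 of July 18, 2024. Barring treatment extensions, sampling was probably complete.

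No new data are needed, since the times of the last four doses are recorded. The cost is slightly more modelling and fewer samples in the raw tables, possibly many fewer for ART if sites followed the 12 h target. That is why samples outside the window should stay in the model.

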11.3.2 Data Analysis

Pharmacokinetics

CVC Exposure: An average steady-state CVC trough concentration will be estimated by ART regimen (INSTI- or NNRTI-based ART) and compared between ART regimens and with historical data for CVC.

ART exposure: An average steady-state ART trough concentration will be estimated pre- and post-CVC/placebo for CVC dosing. Average steady state ART trough concentrations during CVC/placebo for CVC co-administration will be compared a) between those on CVC and those on placebo for CVC (inter-participant comparison) and b) with pre-CVC levels (intra-participant comparison).

Analyses will use time-adjusted linear mixed effect models with measured concentration log-transformed.

Pharmacodynamics

Correlation of CVC exposure to outcomes: A composite time-adjusted CVC exposure estimate over the 24-week study period will be obtained for each participant from the mixed effect modelling based on their measured concentrations at weeks 4, 8, 12, and 24. Associations of these empirical Bayes estimates and the following arterial inflammation outcomes measured will be estimated via Spearman's rank-based correlation.

- Change in most diseased vessel TBR from baseline to week 24
- Change in aortic TBR from baseline to week 24
- Change in carotid artery TBR from baseline to week 24
- Week 24 aortic TBR
- Week 24 carotid artery TBR

11.4 Anticipated Outcomes

Average trough estimates for CVC and each ART will be calculated for comparisons outlined above. Trough estimates for CVC at weeks 4, 8, 12, and 24 will be time adjusted to provide a composite exposure estimate as described above.

12.0 DATA COLLECTION AND MONITORING

12.1 Records to Be Kept

Electronic case report form (eCRF) screens will be made available to sites for data entry. Participants must not be identified by name on any data submitted to the DMC. Participants will be identified by the patient identification number (PID) and study identification number (SID) provided by the ACTG DMC upon randomization.

12.2 Role of Data Management

12.2.1 Instructions concerning entering study data on eCRFs will be provided by the ACTG DMC. Each CRS is responsible for keying the data in a timely fashion.

12.2.2 It is the responsibility of the ACTG DMC to ensure the quality of computerized data for each ACTG study. This role extends from protocol development to generation of the final study databases.

12.3 Clinical Site Monitoring and Record Availability

Monitoring visits may be conducted on-site or remotely. Remote visits may include remote source document verification using methods specified for this purpose by NIAID. Remote monitoring visits may be performed in place of, or in addition to, onsite visits to ensure the safety of study participants and data integrity [47]. The site **must** make available study documents for site monitors to review utilizing a secure platform that is HIPAA and 21 CFR Part 11 compliant. **The Data Management Center will configure Medidata Remote Source Review (RSR) and make it available to all sites. We encourage Sites to use the the DMC provided Medidata RSR platform but other potential** platform options include: Veeva SiteVault, site-controlled SharePoint or cloud-based portal, **and** direct access to Electronic Medical Record (EMR). Other secure platforms that are 21 CFR Part 11 compliant may be utilized, as allowed by the DAIDS Office of Clinical Site Oversight (OCSO).

12.4 Reporting Protocol Deviations

The site principal investigator and staff are responsible for identifying and reporting deviations. If protocol deviations are identified, corrective actions are to be developed by the site and implemented promptly. Protocol deviations must be reported to the IRB/EC per their guidelines.

Refer to the MOPS for the definition of protocol deviation and instructions for completing the study protocol deviation eCRF.

13.0 PARTICIPANTS

13.1 Institutional Review Board (IRB) Review and Informed Consent

This protocol and the [Informed Consent](#) document and any subsequent modifications will be reviewed and approved by the IRB or EC responsible for oversight of the study. A signed consent form will be obtained from the participant (or legal guardian or person with power of attorney for participants who cannot consent for themselves). The consent form will describe the purpose of the study, the procedures to be followed, and the risks and benefits of participation. A copy of the consent form will be given to the participant or legal guardian, and this fact will be documented in the participant's record.

13.2 Participant Confidentiality

All laboratory specimens, evaluation forms, reports, and other records that leave the site will be identified by coded number only to maintain participant confidentiality. All records will be kept locked. All computer entry and networking programs will be done with coded numbers only. Clinical information will not be released without written permission of the participant, except as necessary for monitoring by the ACTG, IRB/EC, FDA, NIAID, OHRP, other local, US, and international regulatory authorities as part of their duties, or the industry supporter or designee.

13.3 Study Discontinuation

The study may be discontinued at any time by the ACTG, IRB/EC, FDA, NIAID, OHRP, other country-specific government agencies as part of their duties to ensure that research participants are protected, or the industry supporter.

14.0 PUBLICATION OF RESEARCH FINDINGS

Publication of the results of this trial will be governed by ACTG policies. Any presentation, abstract, or manuscript will be made available for review by the industry supporter prior to submission.

15.0 BIOHAZARD CONTAINMENT

As the transmission of HIV and other blood-borne pathogens can occur through contact with contaminated needles, blood, and blood products, appropriate blood and secretion precautions will be employed by all personnel in the drawing of blood and shipping and handling of all specimens for this study, as currently recommended by the Centers for Disease Control and Prevention and the National Institutes of Health.

All dangerous goods and materials, including diagnostic specimens and infectious substances, must be transported using packaging mandated by CFR 42 Part 72. Please refer to instructions detailed in the International Air Transport Association (IATA) Dangerous Goods Regulations.

APPENDIX I: RESULTS OF CENICRIVIROC MESYLATE (CVC) STUDIES

Appendix I Table 1

Study Number/Phase	Study Title	Participant Description	Dose & Administration	CVC Formulation	Endpoints
Allergan Study 652-1-104 Phase 1	A phase 1 multiple-dose, cross-over study to assess the potential interaction between TBR-652 and RTV in healthy volunteers	20 healthy adults	50 mg CVC po × 10 days, then 50 mg CVC + 100 mg RTV po × 10 days (CVC administered as 2×25 mg tablets after a standardized meal) [Standardized meal contained approximately 500-700 kcal and <15-20 g fat]	DP3_25 formulation, manufactured by Emerson Resources	1. Plasma PK of CVC with/without RTV 2. Safety, tolerability
Noteworthy Findings:					
RTV significantly increased exposure to CVC (based on ratios of LS geometric means: 2.39-fold increase in Cmax and a 3.55-fold increase in AUC0-24) and reduced exposure to CVC metabolites. There were no clinically important safety findings.					
Allergan Study 652-1-105 Phase 1	A phase 1, open-label, single-dose, randomized, cross-over study to assess the potential interaction between TDF and TBR-652 in healthy volunteers	21 healthy adults	150 mg CVC po, 300 mg TDF, 150 mg CVC po + 300 mg TDF (CVC administered as 6×25 mg tablets after a standardized breakfast) [Standardized breakfast contained approximately 500-700 kcal and <15-20 g fat] 14-day washout between regimens	DP3_25 formulation, manufactured by Emerson Resources	1. Plasma PK of CVC with/without TDF 2. Plasma PK of TDF with/without CVC 3. Safety, tolerability
Noteworthy Findings:					
TDF had no effect on CVC exposure. Co-administration of CVC and TDF did not affect the AUC0-t and AUC0-∞ of TDF, based on the protocol-defined equivalence range of 0.70-1.43. However, co-administration with CVC increased the AUC and Cmax of TDF by approximately 28%-36%, with the 90% CI for the Cmax of TDF falling outside the 0.80-1.25 “no effect” range. There were no clinically important safety findings.					

Study Number/Phase	Study Title	Participant Description	Dose & Administration	CVC Formulation	Endpoints
Allergan Study 652-1-107 Phase 1	A Phase 1, multiple-dose, open-label, crossover study in healthy participants to assess the effect of DRV/r on the PK of CVC	20 healthy adults	Period 1: CVC 50 mg QD po × 10 days after a standardized breakfast Period 2: CVC 50 mg QD po + DRV/r 800/100 mg QD po × 10 days after a standardized breakfast	DP6_50 formulation, manufactured by Bend Research	1. Plasma PK of CVC 2. Safety and tolerability
Noteworthy Findings:					
Co-administration of DRV/r 800/100 mg with CVC 50 mg daily for 10 days resulted in an approximately 2.17-fold increase in plasma CVC Cmax, a 4.17-fold increase in Cmin, and a 3.13-fold increase in AUC0–24.					
Allergan Study 652-1-108 Phase 1	A Phase 1, multiple-dose, open-label, crossover study in healthy participants to assess the effect of ATV/r on the PK of CVC	20 healthy adults	Period 1: CVC 50 mg QD po × 10 days after a standardized breakfast Period 2: CVC 50 mg QD po + ATV/r 300/100 mg QD po × 10 days after a standardized breakfast	DP6_50 formulation, manufactured by Bend Research	1. Plasma PK of CVC 2. Safety and tolerability
Noteworthy Findings:					
Co-administration of ATV/r 300/100 mg with CVC 50 mg daily for 10 days resulted in an approximately 2.55-fold increase in plasma CVC Cmax, a 5.75-fold increase in Cmin, and a 3.89-fold increase in AUC0–24.					

Study Number/Phase	Study Title	Participant Description	Dose & Administration	CVC Formulation	Endpoints
Allergan Study 652-1-109 Phase 1	A Phase 1, multiple-dose, open-label, crossover study in healthy participants to assess the effect of EFV on the PK of CVC and to assess the effect of CVC on the PK of EFV	40 healthy adults (20 in Group 1 and 20 in Group 2)	
Group 1 (effect of EFV on CVC): Period 1: CVC 200 mg QD po after dinner* × 10 days Period 2: CVC 200 mg QD po after dinner* + EFV 600 mg QD po at bedtime × 10 days Period 3: CVC 400 mg QD po after dinner* + EFV 600 mg QD po at bedtime × 10 days (14-day washout between Periods 2 and 3)
 
Group 2 (effect of CVC on EFV): Period 1: EFV 600 mg QD po at bedtime × 10 days Period 2: EFV 600 mg QD po at bedtime + CVC 400 mg QD po after dinner* × 10 days
 
[*Standardized dinner contained 725 kcal, 26 g fat, 89 g carbohydrates, 26 g protein]
	DP6_50 formulation, manufactured by Bend Research	
 1. Plasma PK of CVC (Group 1) 2. Plasma PK of EFV (Group 2) 3. Safety and tolerability
Noteworthy Findings: In Group 1, co-administration of EFV 600 mg with CVC 200 mg daily for 10 days during Period 2 resulted in a significant decrease in CVC exposure compared to CVC alone, with Cmax, Cmin, and AUC0–24 being 23%, 48%, and 43% lower, respectively, for EFV + CVC co-administration compared to CVC alone. Dose adjustment of CVC to 400 mg daily in Period 3 offset the drug interacting effect of EFV 600 mg co-administration with CVC; for Cmax, Cmin, and AUC0–24, the ratios of the LS geometric means (90% CI) were 1.23 (1.12, 1.35), 0.85 (0.71, 1.01), and 0.98 (0.85, 1.12), respectively (i.e., with the 90% CIs including 1.00 for Cmin, and AUC0–24 and within the 0.80–1.25 “no-effect” range for AUC0–τ and within the 0.70–1.43 “equivalence” range for Cmax and Cmin). In Group 2, plasma EFV exposure remained essentially unchanged in the presence of CVC 400 mg daily.					

Study Number/Phase	Study Title	Participant Description	Dose & Administration	CVC Formulation	Endpoints
Allergan Study 652-1-110 Phase 1	A Phase 1, multiple-dose, open-label, crossover study in healthy participants to assess the effect of DTG on the PK of CVC and the effect of CVC on the PK of DTG and on a single dose of midazolam	40 healthy participants (20 in Group 1 and 20 in Group 2)	
Group 1:
 
Period 1: Single dose of midazolam 5 mg po on Day -1 and Day 9 + CVC 150 mg QD po after a standardized breakfast × 10 days (Days 1 to 10)
 
Period 2: CVC 150 mg QD po + DTG 50 mg po QD after a standardized breakfast × 10 days
 
Group 2:
 
Period 1: DTG 50 mg QD po after a standardized breakfast × 10 days
 
Period 2: DTG 50 mg QD po + CVC 150 mg QD po after a standardized breakfast × 10 days
	DP7_150 formulation, manufactured by QS Pharma	
 1. Plasma PK of CVC (Group 1) 2. Plasma PK of DTG administered with and without CVC 3. PK of midazolam and α-hydroxy midazolam 4. Safety and tolerability
Noteworthy Findings: In Group 1, co-administration of DTG 50 mg with CVC 150 mg once daily for 10 days during Period 2 resulted in a significant reduction in plasma CVC exposure (by 28% for Cmax, 23% for Cmin, and 29% for AUC0-24). In Group 2, co-administration of CVC 150 mg with DTG 50 mg once daily for 10 days during Period 2 had no effect on plasma DTG exposure. CVC increased plasma midazolam Cmax and AUC0-∞ by approximately 49% and 84%, respectively, indicating it is a mild inhibitor of CYP3A4. CVC did not result in a meaningful change in plasma α-hydroxymidazolam exposures: there was a 7% decrease in Cmax and an 18% increase in AUC0-∞.					

Study Number/Phase	Study Title	Participant Description	Dose & Administration	CVC Formulation	Endpoints
Allergan Study 652-1-111 Phase 1	A Phase 1, open-label, single-dose, crossover study in healthy participants to assess the bioavailability of a new oral tablet formulation of CVC when administered fasting and after food relative to the current formulation	42 healthy adult participants (14 participants per group)	Group 1: 50 mg CVC: DP6 fed, DP7 fed, DP7 fasting Group 2: 150 mg CVC DP6 fed, DP7 fed, DP7 fasting Group 3: 200 mg CVC DP6 fed, DP7 bedtime Single oral dose of the current CVC formulation (DP6) or the new formulation (DP7) in each of 2 or 3 periods after a standardized breakfast ("fed"), fasting, or ≥ 3 h post dinner ("bedtime"), separated by a washout period of ≥ 10 days.	DP6_50 formulation, manufactured by Bend Research DP7 formulation (DP7_25, 150), manufactured by QS Pharma	
 Relative bioavailability of plasma CVC (current and new formulations) Safety and tolerability Effect of intragastric pH on PK of CVC

Noteworthy Findings:

For comparison of the 50 mg CVC dose administered under fed conditions in the morning, the ratios of LS geometric means for plasma CVC Cmax, AUC0-t, and AUC0- ∞ for the DP7 formulation (Treatment B) relative to the DP6 formulation (Treatment A) were 0.83, 0.72, and 0.79, respectively, with 90% CIs including 1.0. For comparison of the 150 mg CVC dose administered under fed conditions in the morning, the ratios of LS geometric means for plasma CVC Cmax, AUC0-t, and AUC0- ∞ for the DP7 formulation (Treatment E) relative to the DP6 formulation (Treatment D) were 1.22, 0.98, and 1.05, respectively, with 90% CIs including 1.0. The DP7 formulation was significantly better absorbed in the fed than fasting state, particularly at the 150 mg dose. The DP7 formulation administered as a single oral dose of 200 mg at bedtime (Treatment H: DP7 200 mg HS) had an approximately 2-fold higher exposure compared to the DP6 formulation administered as a single oral dose of 200 mg in the morning following a standard breakfast (Treatment G: DP6 200 mg Fed AM); the ratios of LS geometric means for plasma CVC Cmax, AUC0-t, and AUC0- ∞ for the DP7 formulation administered at bedtime (Treatment H) compared to the DP6 formulation after a standardized breakfast (Treatment G) were 1.49, 2.08 and 2.06, respectively.

Study Number/Phase	Study Title	Participant Description	Dose & Administration	CVC Formulation	Endpoints
Allergan Study 652-1-112 Phase 1	A Phase 1, multiple-dose, open-label, crossover study in healthy participants to assess the effect of CVC on the PK of ATV and RTV	20 healthy adults	Period 1: ATV/r 300/100 mg QD po after a standardized breakfast × 10 days (Days 1-10) Period 2: ATV/r 300/100 mg QD po + CVC 50 mg QD po after a standardized breakfast × 10 days (Days 11-20) Period 1 was immediately followed by Period 2 without washout.	DP6_50 formulation, manufactured by Bend Research	1. PK of ATV and RTV with/without CVC 2. Safety and tolerability of CVC with ATV and RTV
Noteworthy Findings:					
CVC had no effect on RTV Cmax or AUC ₀₋₂₄ , although significantly increased exposure to ATV (1.2-fold increase in Cmax, 1.6-fold increase in Cmin, and a 1.3-fold increase in AUC ₀₋₂₄) and RTV Cmin (1.5-fold increase in RTV Cmin).					
Allergan Study 652-1-113 Phase 1	A Phase 1, multiple-dose, open-label, crossover study in healthy participants to assess the effect of CVC on the PK of DRV and RTV	20 healthy adults	Period 1: DRV/r 800/100 mg QD po after a standardized breakfast × 10 days Period 2: DRV/r 800/100 mg QD po + CVC 50 mg QD po after a standardized breakfast × 10 days Period 1 was immediately followed by Period 2 without washout.	DP6_50 formulation, manufactured by Bend Research	1. PK of DRV and RTV with/without CVC 2. Safety and tolerability of CVC with DRV and RTV
Noteworthy Findings:					
Co-administration of CVC 50 mg with DRV/r 800/100 mg daily for 10 days during Period 2 resulted in no meaningful effects of CVC on plasma DRV or RTV exposure. The ratios of LS geometric means for DRV Cmax, Cmin, and AUC ₀₋₂₄ for CVC+DRV/r co-administration compared to DRV alone were 1.02, 0.94, and 0.98, respectively, with 90% CIs including 1.0 and being well within the 0.80–1.25 “no effect” range for all 3 plasma DRV PK parameters.					

Study Number/Phase	Study Title	Participant Description	Dose & Administration	CVC Formulation	Endpoints
Allergan Study 652-2-201 Phase 2a	A double-blind, randomized, placebo-controlled, proof of concept, multiple dose-escalating study to evaluate the antiviral activity, safety, and PK of the CCR5 antagonist CVC in HIV-1-infected, antiretroviral treatment-experienced, CCR5 antagonist-naïve participants	54 adults with R5-tropic HIV-1 8/dose level on CVC 2/dose level on placebo	25 mg (1×25 mg DP3 tablet) 50 mg (2×25 mg DP3 tablets) 75 mg (3×25 mg DP3 tablets) 100 mg (1×100 mg DP4 tablet) 150 mg (6×25 mg DP3 tablets) All administered orally once daily and all provided with a meal. Participants knew to which dose group they were assigned, but were blind to treatment assignment (CVC or placebo)	DP3_25 formulation, manufactured by Emerson Resources DP4_100 formulation, manufactured by Emerson Resources	1. Antiviral activity 2. Safety, tolerability 3. Plasma PK 4. PD 5. Biomarkers of inflammation
Noteworthy Findings: CVC significantly reduced HIV-1 RNA. The median nadir changes from Baseline for the 25, 50, 75, and 150 mg dose groups were -0.7, -1.6, -1.8, and -1.7 log ₁₀ copies/mL, respectively (note that the efficacy and PK results with CVC 100 mg [administered as an alternative formulation] are not shown). CVC significantly increased MCP-1 by up to 340 pg/mL at the 150 mg dose level. Treatment was well tolerated with no dose-limiting AEs.					

Study Number/Phase	Study Title	Participant Description	Dose & Administration	CVC Formulation	Endpoints
Allergan Study 652-2-202 Phase 2b	A Phase 2b randomized, double-blind, double-dummy trial of 100 or 200 mg once-daily doses of CVC or once-daily EFV, each with open-label FTC/TDF, in HIV-1-infected, antiretroviral treatment-naïve, adult participants with only CCR5-tropic virus	143 adults living with HIV, treatment-naïve participants with CCR5-tropic virus Participants were randomized in a 2:2:1 ratio to: CVC 100 mg, CVC 200 mg, or EFV 600 mg (all administered orally QD, but not at the same time, in combination with FTC/TDF).	CVC 100 mg (Phase 2b formulation; administered as 2×50 mg tablets + 2× CVC matching placebo tablets) and EFV placebo CVC 200 mg (Phase 2b formulation; administered as 4×50 mg tablets) and EFV placebo EFV 600 mg and 4 × CVC matching placebo tablets CVC/placebo administered following a low-fat breakfast; EFV/placebo on an empty stomach at bedtime	DP6_50 formulation, manufactured by Bend Research	
 1. Efficacy 2. Safety, tolerability 3. Plasma PK 4. PD 5. Biomarkers of inflammation and immune function 6. Metabolic parameters
Noteworthy Findings: CVC when administered as either 100 mg + FTC/TDF or 200 mg + FTC/TDF was effective and well tolerated over 48 weeks in participants living with HIV, antiretroviral treatment-naïve adult participants with only CCR5-tropic virus. A greater proportion of CVC- than EFV-treated participants completed the study, 42 (71%), 41 (73%), and 17 (61%) for the CVC 100 mg, CVC 200 mg, and EFV treatment arm, respectively. The percentage of participants with virologic success, defined as HIV-1 RNA <50 copies/mL (using the FDA Snapshot analysis and the ITT population), was comparable among the 3 treatment arms at Week 24 (the primary efficacy endpoint: 76% with CVC 100 mg, 73% with CVC 200 mg, and 71% with EFV) and higher in the CVC arms than in the EFV arm at Week 48 (68% with CVC 100 mg, 64% with CVC 200 mg, and 50% with EFV). A dose-response was observed with CVC in increases over time of MCP-1, the ligand of CCR2, which is a chemokine receptor found on monocytes, suggesting potent CCR2 blockade. Additionally, a decrease over the first 48 weeks was observed for sCD14, an established biomarker of monocyte activation, in both CVC treatment arms, while an increase was observed for sCD14 in the EFV arm during the same observation period. CVC showed a favorable safety profile with fewer treatment-related AEs, fewer AEs of at least Grade 3 in severity, and fewer AEs leading to discontinuations compared to EFV. Both doses of CVC (100 mg and 200 mg) were well tolerated and no apparent dose-relationship based on safety data or dose-limiting toxicities were observed.					

Study Number/Phase	Study Title	Participant Description	Dose & Administration	CVC Formulation	Endpoints
Allergan Study 652-2-203 Phase 2b	CENTAUR: Efficacy and Safety Study of Cenicriviroc for the Treatment of Nonalcoholic Steatohepatitis (NASH) in Adult Participants with Liver Fibrosis	289 adults with NASH with liver fibrosis (biopsy-diagnosed NASH with NAS ≥ 4 and liver fibrosis (Stage 1 to 3 [NASH CRN system]), who are at increased risk of disease progression. Randomization 1:1 stratified by NAS at Screening (4 or ≥ 5) and fibrosis stage (≤ 2 or > 2).	150 mg tablets and matching placebo tablets	DP7_150 formulation Manufactured by QS Pharma	The primary efficacy endpoint: Hepatic histological improvement as measured by the NAFLD Activity Score (NAS) at Year 1 relative to the Screening biopsy.

Noteworthy Findings:

Year 1: Twenty-three (15.9%) participants in the CVC group met the primary efficacy endpoint compared to 27 (18.8%) participants in the placebo group. The difference between the treatment groups was not statistically significant in the ITT population ($p=0.5194$).

In the ITT population, 11 participants (7.6%) in the CVC group compared with 8 participants (5.6%) in the placebo group had complete resolution of steatohepatitis and no concurrent worsening of fibrosis stage at Year 1 relative to the Screening biopsy ($p=0.4941$). These results did not change after prespecified sensitivity analyses.

Importantly, in the Year 1 analysis, 29 participants (20.0%) in the CVC group compared with 15 participants (10.4%) in the placebo group had improvement in fibrosis by at least 1 stage and no worsening of steatohepatitis at Year 1 relative to the Screening biopsy in the ITT population set ($p=0.0234$). A higher proportion of participants in the CVC group (29%) compared with the combined placebo group (19%) had an improvement of at least 1 stage at Year 1 per the NASH CRN staging system. Furthermore, at Year 1, the proportion of participants achieving the more stringent endpoint of ≥ 2 -stage improvement in fibrosis AND no worsening of steatohepatitis for CVC or placebo = 8.2% (8/98) and 3.1% (3/96), respectively, in the ITT population excluding participants with baseline NASH CRN fibrosis Stage 1.

Year 2: At the end of the first year of treatment, a total of 242 participants remained in the study and entered Year 2 according to their treatment assignment at randomization (121, 61, and 60 participants in the CVC/CVC, placebo/CVC, and placebo/placebo groups, respectively). Given the lack of apparent effect of CVC treatment on the NAS or resolution of steatohepatitis at Year 1, the results presented below describe findings from prespecified analyses focused on the endpoint of improvement in fibrosis stage (by ≥ 1 stage or by ≥ 2 stages) AND no worsening of steatohepatitis in the ITT population.

Overall, the results from the final Year 2 analysis confirmed the clinically meaningful antifibrotic effect of CVC treatment observed in the Year 1 primary analysis. Twice as many CVC-treated participants achieving ≥ 1 -stage improvement in fibrosis at Year 1 (CVC/CVC group) maintained this benefit at Year 2 compared to placebo (60% vs 30%, respectively). A higher proportion of Year 1 placebo nonresponder participants who received CVC (placebo/CVC group) experienced an improvement in fibrosis by ≥ 1 stage AND no worsening of steatohepatitis compared with participants who remained on placebo (placebo/placebo group) from Year 1 to Year 2 (24.4% vs 17.1%, respectively). In this analysis, improvement in fibrosis by ≥ 1 stage regardless of effect on steatohepatitis was reported in 39.0% of placebo/CVC participants versus 28.6% of placebo/placebo participants.

A similar and consistent antifibrotic response was observed in the pooled analysis of participants treated with CVC for 1 year (participants in the CVC/CVC group who received CVC during Year 1 and the placebo/CVC group who received CVC during Year 2) compared with participants treated with placebo for 1 year (placebo/placebo

Study Number/Phase	Study Title	Participant Description	Dose & Administration	CVC Formulation	Endpoints
group; data from Year 1): improvement in fibrosis by ≥ 1 stage AND no worsening of steatohepatitis (19.9% vs 11.1%); improvement in fibrosis by ≥ 1 stage regardless of effect on steatohepatitis (27.7% vs 16.7%). Furthermore, consistent with observation at Year 1, a higher proportion of participants receiving CVC relative to participants receiving placebo (9.3% [7/75] in the CVC/CVC group versus 2.7% [1/37] in the placebo/placebo group) achieved ≥ 2 -stage improvement in fibrosis AND no worsening of steatohepatitis at Year 2.					
Tobira Study 652-2-204- Phase 2a	ORION: Effect of CCR2 and CCR5 Antagonism by Cenicriviroc on Peripheral and Adipose Tissue Insulin Sensitivity in Adult Obese Participants with Prediabetes or Type 2 Diabetes Mellitus and Suspected Non-Alcoholic Fatty Liver Disease (NAFLD)	45 adult obese participants (BMI ≥ 30 kg/m 2) with prediabetes or T2DM and suspected NAFLD; randomized 1:1 to active drug or placebo (50 participants planned, 45 enrolled)	150 mg tablets and matching placebo tablets once daily for 24 weeks	DP7_150 formulation Manufactured by QS Pharma	1. Efficacy 2. Safety, tolerability 3. Plasma PK 4. PD 5. Biomarkers of inflammation and immune function Metabolic parameters
Noteworthy Findings: There was no observed therapeutic effect of CVC on peripheral and adipose tissue insulin sensitivity as compared to placebo. CVC was well tolerated and resulted in a lower incidence of AEs compared with placebo. No new safety signals were observed.					
Tobira Study 652-205 Phase 2	PERSEUS: A Phase 2 Proof of Concept Study Investigating the Preliminary Efficacy and Safety of Cenicriviroc in Adult Participants with Primary Sclerosing Cholangitis (PSC)	24 adult participants with PSC	150 mg tablets once daily for 24 weeks	DP7_150 formulation Manufactured by QS Pharma	1. Efficacy 3. Safety, tolerability
Noteworthy findings: In adults with PSC, treatment with CVC 150 mg QD for 24 weeks resulted in a modest (median of 18%) decrease in the surrogate endpoint of ALP. No new safety signals were observed					

Study Number/Phase	Study Title	Participant Description	Dose & Administration	CVC Formulation	Endpoints
